## 5.8.4 Electrocardiogram

Local reading:

12-Lead ECG will be recorded for all subjects in both study parts as follows:

- Screening Visit
- Cycle 1, 2, 3 and 4 at: prior to AGI-134 administration (up to 1 hour before dose) and 2 hours post dose (± 30 minutes). In Cycles 1 and 4, ECG printouts for safety assessment may be taken from the Holter recording device.
- Termination/Early Termination Visit

## Central reading:

 Cycle 1 and 3: 12-lead ECG Holter recording device will be connected to the subject 1-2 hours prior to AGI-134 administration and record ECG consecutively for at least 24 hours after AGI-134 administration.

## 5.8.5 Physical Examination and Symptom-Directed Physical Examination

Complete physical examination (PE) will be conducted at screening and at Termination/ET. PE will include assessment of the following body systems: Head, neck, thyroid, respiratory, cardiovascular, ophthalmologic, gastrointestinal, hepatic, musculoskeletal system, dermatological, lymph nodes, neurological system and, where appropriate, other body systems as indicated in the study schedule.

A limited, symptom-directed PE (Directed PE) should be performed on Day 1 pre-dose of each cycle. During a Directed PE, particular attention should be focused on identifying possibly drug-related AEs. It is important to carefully inspect the lesion's site of injection and site biopsy. Changes in PE since last visit will be assessed and, if assessed as clinically significant, it should be reported within the eCRF as an AE. Information about the PE must be presented in the source documentation at the study site. Significant findings that are present prior to the investigational product administration must be included in the Relevant Medical History/ Current Medical Conditions eCRF page. Significant findings made after investigational product administration, which meet the definition of an AE, must be recorded on the AE eCRF module.

#### 5.8.6 Laboratory Safety Assessment

All clinical laboratory safety assessments, listed below, will be performed by local laboratories at the participating sites at Screening and at different time points during treatment depending on the specific assessment. Pre-dose laboratory procedures may be conducted up to 4 hours prior to dosing.

agalin A subsidiary of Bio	nnune DLINERX	PRIVILEGED & CONFIDENTIAL
Investigational Product: AGI-134		Protocol No. AGI-134.FIM.101
Phase: I/IIa	doses of AGI-134 in unresectable/metastatic solid tumours.	Version 6.1 31 May 2021

Laboratory safety sampling will include the parameters listed below. The exact time points for each of the tests are specified in the SoA (APPENDIX A). Safety Biomarker will be assessed as well, as defined in Table 2.

Laboratory tests for haematology, chemistry, urinalysis and others are specified in Table 1.

Table 1: Laboratory Tests

Haematology	Chemistry	Urinalysis	Other
Haematocrit	Albumin	Blood	Follicle Stimulating Hormone (FSH)
Haemoglobin	Alkaline phosphatase	Glucose	Serum or urine pregnancy test
Platelet count	Alanine aminotransferase (ALT)	Protein	Hepatitis B Surface Antigen [HBsAg] reactive
WBC (total and differential)	Aspartate aminotransferase (AST)	Specific gravity	Hepatitis C (e.g., HCV RNA [qualitative]
RBC	Calcium	Microscopic examination	HIV1 and 2
	Chloride		TSH, T3 (free or total) and freeT4
	Creatinine		PT/INR and aPTT
	Glucose		
	Phosphorus		
	Potassium		
	Sodium		
	Total Bilirubin		
	Direct Bilirubin		
	Total protein		
	Blood Urea Nitrogen		
	Lactic dehydrogenase (LDH)		

Table 2: Safety Biomarkers

Test	Scientific Rationale	Frequency of Test	Levels Quantified in Terms of Actionable Items
Anti-Gal IgE	Acute hypersensitivity may be caused by presence of serum anti-Gal IgE antibodies in humans, which are associated with allergies to red meat and induced by bites from the Lone Star Tick, Amblyomma americanum .	Screening period (Exclusion Criteria)  Blood for anti-Gal IgE on Cycle 3 before injection of AGI-134 (timepoint selected based on isotype switching kinetics)	Positive detection of IgE anti- Gal at Screening will exclude the subject from the study. If IgE anti-Gal is detected during assessment at Cycle 3, dosing with AGI-134 will be discontinued.

Laboratory safety test abnormalities that arise after investigational product administration will be repeated as clinically indicated until the values return to normal or until the aetiology has been determined and the condition considered stable. Abnormal laboratory test results that are considered to be clinically significant by the Site PI will be reported as AEs in the AE eCRF module.

agalin A subsidiary of Bio	nnune DLINERX	PRIVILEGED & CONFIDENTIAL
Investigational Product: AGI-134		Protocol No. AGI-134.FIM.101
Phase: I/IIa	doses of AGI-134 in unresectable/metastatic solid tumours.	Version 6.1 31 May 2021

A laboratory abnormality will not be considered an AE unless it fulfils one of the following:

- It is clinically significant according to the PI's judgement
- Intervention is required
- Changes in dose are required (decrease, discontinued, interrupted)
- · Other treatment/therapy is required
- Associated with other diagnoses

Laboratory results will be reported to the PI or designee who will review, sign and date abnormal laboratory findings for clinical significance. The PI will note any laboratory test results of clinical concern or values that were outside normal ranges and provide details of the relationship to the investigational product and the action taken. If a change in a laboratory value represents a medical condition, the medical condition will be listed in the AE record. If no correlation is possible, the direction of change (increase or decrease) in addition to the actual value will be recorded.

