### 7 SAFETY PHARMACOVIGILENCE

#### 7.1 Adverse Events

An AE is defined in the International Conference on Harmonisation (ICH) E6 as "any untoward medical occurrence in a subject or clinical investigation subject administered a pharmaceutical product and which does not necessarily have a causal relationship with this treatment. An AE can therefore be any unfavourable and unintended sign (including an abnormal laboratory finding), symptom or disease temporally associated with the use of a medicinal (investigational) product, whether or not related to the medicinal (investigational) product."

An abnormal result of diagnostic procedures including abnormal laboratory findings will be considered an AE if it fulfils one or more of the following:

- Results in subject's withdrawal by the PI
- Is associated with an SAE
- · Is associated with clinical signs or symptoms
- Is considered by the PI to be of clinical significance

A new condition or the worsening of a pre-existing condition will be considered an AE.

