# 8.2.2 Analysis of Safety and Tolerability

Safety parameters (vital signs and laboratory results) will be summarised in listings and presented in tables as changes from Baseline.

ECG examinations results will be displayed in descriptive tables provide the frequency of subjects with abnormal findings for each schedule visit.

AEs will be coded using the latest version of MedDRA (currently version 24.0) and presented in tables by system organ class (SOC), HLT and preferred term. The worst severity grade of AEs, as determined by the latest version of the NCI-CTCAE (currently version 5.0), and their relationship to investigational product will be analysed by SOC, High Level Terms and Preferred Term.

The action taken, and outcome will also be analysed.

By-subject list of AEs, severity grade and relationship will be presented in time-sequence manner using the latest version of NCI-CTCAE (currently 5.0) with SOC, High Level terms and Preferred Term. The number and incidence of subjects experiencing toxicity will be tabulated by worst severity grade in each MedDRA term. The proportion of subjects experiencing toxicity  $\geq$  Grade 3 for each type of toxicity will be calculated.

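### Sections 5.8.6 and 7.1 give different tests for when a laboratory abnormality is an AE, and the Grade 3 or higher proportions in Section 8.2.2 appear to rest on AE records alone

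*Combined protocol and SAP*

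**What the plan says.** Section 5.8.6 (Laboratory Safety Assessment) states: "A laboratory abnormality will not be considered an AE unless it fulfils one of the following". The list is the investigator's judgement of clinical significance, a need for intervention, a dose change (decrease, interruption or discontinuation), a need for other treatment, and association with another diagnosis.

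Section 7.1 (Adverse Events) states: "An abnormal result of diagnostic procedures including abnormal laboratory findings will be considered an AE if it fulfils one or more of the following". Its list is withdrawal by the investigator, association with an SAE, association with signs or symptoms, and the investigator's judgement of clinical significance.

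Section 8.2.2 plans two kinds of output. For the data themselves: "Safety parameters (vital signs and laboratory results) will be summarised in listings and presented in tables as changes from Baseline". For graded toxicity: "The number and incidence of subjects experiencing toxicity will be tabulated by worst severity grade in each MedDRA term", followed by a proportion at Grade 3 or higher for each type of toxicity. That second plan sits in the paragraph that opens with the by-subject AE list. No data source is named for it.

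Section 8.2 says that a detailed SAP prevails where its methods differ from that section. The combined document as supplied contains no separate SAP text.

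**The concern.** The two lists decide what a site enters as an AE. If they differ and neither is given precedence, the same laboratory result can be entered at one site and not at another, with both following the protocol. Laboratory safety tests are run and judged locally (Section 5.8.6), at about 15 sites (Section 10.1). This is a risk; the documents do not show that it has happened.

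The SAP precedence clause would not remove it. That clause covers the methods of Section 8.2, not what sites record, and an event never entered as an AE cannot be put back into AE tables by an analysis rule.

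Safety and tolerability are part of the primary endpoint (Section 2.2.1). The graded toxicity tables are the descriptive evidence for it, so how laboratory toxicity enters them should be settled in advance.

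**Working it through.** The documents give no laboratory-toxicity rate or threshold to reproduce, so the check is mainly a comparison of the passages.

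**1. The two lists side by side**

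| Criterion | 5.8.6 | 7.1 |
|---|---|---|
| Clinically significant to the investigator | listed | listed |
| Intervention or other treatment needed | listed | not listed |
| Dose decreased, interrupted or discontinued | listed | partial overlap with withdrawal |
| Linked to another diagnosis | listed | not listed |
| Leads to withdrawal | partial overlap with discontinuation | listed |
| Linked to an SAE | not listed | listed |
| Linked to signs or symptoms | not listed | listed |

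The shared criterion reads "It is clinically significant according to the PI's judgement" in one section and "Is considered by the PI to be of clinical significance" in the other.

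**2. Where the lists disagree.** Treat each list as a complete test over these seven criteria, giving 2^7 = 128 patterns.

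- Significance present: 64 patterns, all AEs under both lists.
- Significance absent: 8 × 8 = 64 patterns. Section 5.8.6 met and 7.1 not: 7 × 1 = 7. Section 7.1 met and 5.8.6 not: 1 × 7 = 7.
- Total disagreement: 7 + 7 = 14 of 128, every one with significance judged absent. The patterns are not equally likely, so 14/128 is not a rate.

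**3. Which disagreements are contradictions.** Section 5.8.6 states a necessary condition and Section 7.1 a sufficient one. They contradict each other only when 7.1 is met and 5.8.6 is not, which is seven patterns. If withdrawal is read as a form of dose discontinuation, this leaves SAE, symptoms or both: 2^2 − 1 = 3 patterns. So "Is associated with clinical signs or symptoms" can make a value an AE that Section 5.8.6 says is not one. In the mirror case, a value meeting "Intervention is required" but nothing in 7.1, Section 5.8.6 allows an AE, while 7.1 neither lists nor excludes it.

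**4. What feeds the Grade 3 or higher proportion.** Section 8.2.2 tabulates by MedDRA term, the protocol describes only AEs as MedDRA-coded, and Section 7.1 uses toxicities and AEs interchangeably when it defines grades. AE-based counting is therefore the best reading. The supplied text plans neither CTCAE grading of all laboratory values nor a grade-shift table. A numerically Grade 3 or higher value that is judged not significant and meets no other criterion is outside the AE record under both lists. It appears only in listings and change-from-Baseline summaries.

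**5. Illustrative size.** Section 8.1 gives a Part 1 maximum of 24, which reproduces as 4 × 6, and about 35 in Part 2. The synopsis gives about 10 in the melanoma sub-population. One reclassified subject moves a proportion by 100/n points:

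- n = 6: 16.7
- n = 10: 10.0
- n = 24: 4.2
- n = 35: 2.9
- n = 24 + 35 = 59: 1.7

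Exact (Clopper-Pearson) 95% intervals at n = 35 are 0/35 = 0% (0 to 10.0), 1/35 = 2.9% (0.1 to 14.9) and 2/35 = 5.7% (0.7 to 19.2).

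**6. Decision rules.** Section 8.3.3 takes in abnormal laboratory values directly and requires a DLT to be clinically significant. The Part 1 expansion trigger (Section 8.3.1) also requires clinical significance. Where the investigator makes that call, the event is an AE under both lists. The Part 2 rule that stops accrual above 30% uses the DLT definition, so the same holds.

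**The case against.** The case against is substantial, and most of it limits how far the point can be taken.

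- A reader might infer that a primary laboratory-toxicity rate is at stake. None is defined: the primary endpoint is safety and tolerability with MTD and RP2D, and no laboratory proportion or threshold is attached to it.
- A reader might infer that dose decisions could change. By step 6 they do not turn on the choice of list, although they still depend on a judgement of clinical significance.
- A Grade 3 electrolyte value that is corrected but called not significant may look like a contradiction. It is not, because Section 7.1 does not say that only its own criteria make an AE, and it opens with the broad ICH definition, which covers abnormal laboratory findings.
- Even in the outright conflict, the SAE or an untoward symptom would be recorded in its own right. Section 5.8.6 also sends a laboratory change that represents a medical condition to the AE record as that condition.
- It would be wrong to say that individual high-grade values are hidden. Section 8.2 requires individual listings, with minimum and maximum in the continuous summaries. What is not stated is a graded count.
- AE-only counting is an inference, and an SAP could specify laboratory grading.
- The figures in step 5 are simply 1/n and say nothing about how often reclassification happens.

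All of this stands. It leaves the two unreconciled lists and the lack of a stated graded laboratory analysis. DLT review does not fill that gap: it ends at Cycle 1 Day 21, and it exempts Grade 3 electrolyte abnormalities.

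**Conclusion.** The point holds as a cheap improvement. Sections 5.8.6 and 7.1 give different tests, conflict outright in a narrow class of cases, and carry no rule of precedence. On the best reading of Section 8.2.2, the descriptive laboratory-toxicity rates that support the primary safety endpoint omit Grade 3 or higher values that the investigator judges not significant and that meet no other criterion.

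The size is unknown, because the documents give no basis for the number of subjects affected. Two assumptions carry the conclusion: that toxicity in Section 8.2.2 means recorded AEs, and that clinical significance in the DLT definition is judged by the investigator. The documents do not support extending it to MTD, RP2D, DLT counts or the Part 2 stopping rule.

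**What to change.** 1. Put one list, the union of the two, in both Sections 5.8.6 and 7.1: clinical significance, intervention, dose change, other treatment, other diagnosis, withdrawal, associated SAE, and signs or symptoms. Use the same verb in both places, so that the list is both necessary and sufficient.
2. In Section 8.2.2, name AE records as the source of the existing toxicity tables. Beside them, add CTCAE grades derived by program from the laboratory values in Table 1, with shift tables from baseline to worst grade and the proportion of subjects at Grade 3 or higher for each analyte. State in advance which analytes can be graded from the numerical result alone.

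The values are already collected, and Section 9.13 has laboratories supply reference ranges where applicable. The cost is wording and routine programming. The reported Grade 3 or higher laboratory rate may come out slightly higher, and the programmed tables will not match the AE tables exactly; a footnote should say why.

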#### 5.9 ECOG Performance Status

ECOG performance status (see APPENDIX C) will be collected at each visit, including Termination. ECOG performance assessment should be performed prior to drug administration.

## 5.10 Pharmacodynamic Evaluations

The pharmacodynamic assessments, listed below in Table 3, will be performed by either the local laboratory at the participating sites and/or designated central laboratories according to the Laboratory Manual. The techniques and specific markers for assessments will be defined in the Laboratory Manual.

Table 3: Pharmacodynamic and Biomarkers Assessments

Test	Scientific rationale	Frequency of test
HLA and MHCII Haplotyping	Biomarker for immune response	Cycle 1 (pre-dose)
DNA isolation (MSI/dMMR/TMB/WES ) blood	Biomarker for immune response	Cycle 1 (pre-dose)
DNA isolation (MSI/dMMR/TMB/WES ) tissue	Biomarker for immune response	Baseline
CH50	Biomarker for immune response	Cycle 1 (pre-dose)
C5a	Biomarker for immune response	Cycle 1 (pre-dose, 2h and 6h post dose), Cycle 2 (pre-dose and 2h post dose), Cycle 3 (pre-dose and 2h and 6h post dose) and Cycle 4 (pre-dose and 2h post dose)
Flow cytometry	Biomarker for immune response	Cycle 1 (pre-dose and 24h post dose), Cycle 2 (pre-dose), Cycle 3 (pre-dose and 24h) and Termination

Protocol AGI-134.FIM.101 CONFIDENTIAL Page 56 of 108

agalin A subsidiary of Bio	DINE X	PRIVILEGED & CONFIDENTIAL
Investigational Product: AGI-134		Protocol No. AGI-134.FIM.101
Phase: I/IIa		Version 6.1 31 May 2021

Test	Scientific rationale	Frequency of test
Cytokines	Biomarker for immune response	Cycle 1 (pre-dose, 2, 6, 12, and 24h), Cycle 3 (pre-dose, 2, 6, 12, 24h post dose) and Termination
PBMCs isolation + cryopreservation	Biomarker for immune response	Cycle 1 (pre-dose and 3 days post injection), Cycle 2 (pre-dose), Cycle 3 (pre-dose) and Termination
Anti-Gal IgG/IgM	Biomarker for immune response	Cycle 1 (pre-dose and Day 8), Cycle 2 (pre-dose), Cycle 3 (pre-dose), Cycle 4 (pre-dose) and Termination
Anti-Gal Sub classing	Biomarker for immune response	Cycle 1 (pre-dose), Cycle 2 (pre-dose), Cycle 3 (pre-dose), Cycle 4 (pre-dose) and Termination
TCR sequencing blood	Biomarker for immune response	Cycle 1 (pre-dose), Cycle 3 (pre-dose) and Termination
TCR sequencing tissue	Biomarker for immune response	Baseline, Cycle 3 (pre-dose) and Termination
IHC/H&E/Multiomyx	Biomarker for immune response	Baseline, Cycle 1 (Day 3), Cycle 3 (predose) and Termination
RNA isolation (Gene expression/sequencing) blood	Biomarker for immune response	Cycle 1 (pre-dose and Day 3), Cycle 3 (24h post-dose) and Termination
RNA isolation (Gene expression/sequencing) tissue	Biomarker for immune response	Baseline, Cycle 1 (Day 3), Cycle 3 and Termination

## 5.11 Planned Genetic Analysis

Genetic analysis will be performed on blood and on available biopsy samples. Understanding genetic determinants of drug response is an important endeavour during medical research. This research will evaluate whether genetic variation within a clinical study population correlates with response to the treatment(s) under evaluation.

## 5.12 Efficacy Assessments

Response will be assessed by the PI using RECIST v1.1 (see APPENDIX B). Assessments should be performed by the same evaluator, if possible, to ensure internal consistency across visits. Results must be reviewed by the PI before dosing at the next cycle. Please refer to the *Imaging Manual* for more details.

Subjects will undergo tumour assessments at different timepoints as described below:

- Screening Visit
- Cycle 3 (week 9) and further every 9 weeks (weeks 18, 27, 36, 45) including Termination/Early Termination Visit

Protocol AGI-134.FIM.101 CONFIDENTIAL Page 57 of 108

10		PRIVILEGED & CONFIDENTIAL
Investigational Product: AGI-134		Protocol No. AGI-134.FIM.101
Phase: I/IIa		Version 6.1 31 May 2021

If radiologic imaging verifies initial PD, at PI's discretion, tumour assessment can be repeated ≥4 weeks later and no later than the next schedule CT scan in order to confirm PD with the option of continuing treatment as described below.

All measurable and evaluable lesions should be assessed and documented at Screening. Tumour assessments performed as standard of care prior to obtaining informed consent and within 28 days prior to initiation of study treatment do not have to be repeated at Screening.

The same method of assessment and the same technique should be used to characterise each identified and reported lesion at Baseline and during follow-up. Imaging-based evaluation should always be done rather than clinical examination unless the lesion(s) being followed cannot be imaged but are assessable by clinical exam.

If a CT scan for tumour assessment is performed in a positron emission tomography (PET)/CT scanner, the CT acquisition must be consistent with the standards for a full contrast diagnostic CT scan.

All measurable and evaluable lesions should be re-assessed at each subsequent tumour evaluation. The same radiographic procedures used to assess disease sites at Screening should be used for subsequent tumour assessments (e.g., the same contrast protocol for CT scans).

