- 16. Has received other experimental therapies or used an investigational device within 28 days of the first dose of treatment
- 17. Has had prior chemotherapy, targeted small molecule therapy, or radiation therapy within 14 days before first AGI-134 administration or has not recovered from treatment related AE> Grade 19
- 18. Has had a prior anti-cancer monoclonal antibody (mAb) within 28 days before first AGI-134 administration or who has not recovered from AE > Grade 1.
- 19. Is pregnant or breastfeeding or expecting to conceive or father children within the projected duration of the study, starting with the Screening visit through 120 days after the last dose of study treatment. Women with a positive pregnancy test within 72 hours from Baseline.
- 20. Has unstable angina, new onset angina within the last 3 months, myocardial infarction within the last 6 months, uncontrolled atrial fibrillation, or current congestive heart failure with New York Heart Association Class III or higher.
- 21. Has a known current additional malignancy that is progressing or requires active treatment. Exceptions are non-melanoma skin lesions, adequately treated basal cell or squamous cell carcinoma that has undergone potentially curative therapy or carcinoma in situ of the cervix.
- 22.  $O_2$  saturation < 92% (on room air).
- 23. Has an underlying medical condition that would preclude study participation or other psychological, social or physical examination (PE) finding or a laboratory abnormality that the PI considers would make the subject a poor study candidate or could interfere with protocol compliance or the interpretation of study results.
- 24. Has known psychiatric or substance abuse disorders that would interfere with cooperation with the requirements of the study.

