## **Screening Procedures:**

- ICF signature
- Inclusion/Exclusion Criteria review
- Collection of demographic data
- Collection of medical history
- Collection of disease history (including genetic information, dMMR/MSI/TMB)
- Collection of disease treatment history
- Review of prior (up to one year) and concomitant medications
- AE recording
- 12-lead electrocardiogram (ECG) local reading
- Full physical examination
- Vital signs (blood pressures, pulse rate, O2 saturation, oral temperature in °C, respiratory rate)
- Weight
- Height
- Urinalysis
- ECOG performance status
- Blood will be drawn for:
  - o Serum pregnancy test
  - o FSH for women who reported menopause for less than two years
  - o Disease markers according to each subject's disease
  - HPV status for relevant indications (HPV status assessment should be performed at local lab in case no available status from the time of diagnosis)
  - PT/INR and Activated Partial Thromboplastin Time (aPTT)
  - CBC with differential
  - Biochemistry panel
  - o T3, free T4 and thyroid stimulating hormone (TSH)
  - o HIV, HBV and HCV serology

<sup>10 For subjects on anticoagulant treatment, coagulation test should be performed within 24 before the injection and biopsy at Baseline. Anticoagulants should be stopped for injection and biopsy according to institutional guidelines.

<sup>11 The coagulation test should be within normal limits unless the subjects are being treated with an anticoagulant in which case the values allowed for injection and biopsy as well as the timing to stop anticoagulants before injection and biopsy will be determined at each site according to institutional guidelines.

agalin A subsidiary of BIO		PRIVILEGED & CONFIDENTIAL
Investigational Product: AGI-134		Protocol No. AGI-134.FIM.101
Phase: I/IIa	doses of AGI-134 in unresectable/metastatic solid tumours.	Version 6.1 31 May 2021

- o Blood for anti-Gal IgE
- Tumour imaging. A standard of care imaging performed prior to ICF signature, which were done according to the imaging manual guidelines (Please refer to the *Imaging Manual* for more details) and are within the screening window will be allowed for eligibility.
- RECIST v.1.1 assessment

Subjects may be rescreened after consultation with the Sponsor.

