#### 6.7.2 Prohibited Concomitant Medications

Subjects are prohibited from receiving the following medications during the Core study, beginning at Screening Visit until Termination Visit (week 54) or disease progression, whichever comes first:

- Systemic glucocorticoids for any purpose other than to modulate an event of suspected immunologic aetiology or for systemic and local reactions secondary to the treatment. The use of physiologic doses of corticosteroids may be approved after consultation with the Sponsor. Note: Inhaled steroids are allowed for management of asthma, and dermatological formulations are allowed to reduce the intensity of injection-site reactions.
- Therapy for the disease under study:
  - Antineoplastic systemic chemotherapy or biological therapy
  - Immunotherapy or other therapy not specified in this protocol

20		PRIVILEGED & CONFIDENTIAL
Investigational Product: AGI-134		Protocol No. AGI-134.FIM.101
Phase: I/IIa		Version 6.1 31 May 2021

- Chemotherapy not specified in this protocol
- Investigational agents other than AGI-134
- Radiation therapy: localised radiation therapy may be considered on an exceptional case by case basis after consultation with the Sponsor.

During the Long-Term Follow-Up period, subjects who have no disease progression should be followed up until disease progression, new cancer treatment or withdraw consent. Subjects may receive other treatments following progression and/or upon investigator's and/or the subject's primary physician decision.

For subjects who, in the assessment of the PI, require the use of any of the aforementioned treatments for clinical management, the study continuation should be discussed with the Sponsor's Medical Monitor.

The Exclusion Criteria describes other medications that are prohibited in this study.

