### 2 METHODS FOR ASSESSING LESIONS

All measurements should be recorded in metric notation, using calipers if clinically assessed. All Baseline evaluations should be performed as close as possible to the treatment start and never more than 4 weeks before the beginning of the treatment.

The same method of assessment and the same technique should be used to characterise each identified and reported lesion at Baseline and during the study. Imaging-based evaluation should always be the preferred option.

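### A pre-consent scan can serve as the RECIST baseline even when chemotherapy or targeted therapy was given after it, so shrinkage from that treatment could count towards response to AGI-134

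*Combined protocol and SAP*

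**What the plan says.** **Which scan may be the baseline.** Section 5.12 allows tumour assessments done as standard of care before consent and says that those "within 28 days prior to initiation of study treatment do not have to be repeated at Screening". The Screening list in Section 5.1 agrees: images that follow the Imaging Manual and "are within the screening window will be allowed for eligibility". Appendix B, Section 2, asks for baseline evaluation near the start of treatment and "never more than 4 weeks before the beginning of the treatment".

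**Which prior therapy is excluded, and when.** In Section 4.2, criterion 17 excludes a subject who "Has had prior chemotherapy, targeted small molecule therapy, or radiation therapy within 14 days before first AGI-134 administration". The windows are longer for antibodies (criterion 18: "Has had a prior anti-cancer monoclonal antibody (mAb) within 28 days before first AGI-134 administration") and for experimental agents (criterion 16: "Has received other experimental therapies or used an investigational device within 28 days of the first dose of treatment"). Section 6.7.2 prohibits other treatment of the disease on study, "beginning at Screening Visit until Termination Visit (week 54) or disease progression, whichever comes first".

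**How response is measured.** Under Appendix B, Section 4.1, partial response is a fall of at least 30% in the sum of target lesions from the Baseline sum. Progression is a rise of at least 20% and at least 5 mm from the smallest sum on study. Tables 6 and 7 in Appendix A schedule RECIST at Screening and next in Cycle 3. The Baseline visit list in Section 5.2 has no lesion measurement.

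**The concern.** The scan may be up to 28 days old, while three classes of treatment are excluded only for the last 14. Nothing in the protocol ties the scan date to the date of the last prior therapy, and progression on or after that therapy is not a general entry condition in Section 4.1. The main skin melanoma group must have progressed, but on immunotherapy, and earlier chemotherapy or targeted therapy is allowed.

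The study has no control arm, so the baseline sum is the reference for every RECIST response. If treatment given between the scan and the first dose shrinks the target lesions, the reference sum is too high. Part of the fall seen at Week 9 then belongs to the earlier treatment. The same inflated reference can also hide growth that began after AGI-134 was started. Un-injected lesions used to judge an abscopal effect are exposed in the same way.

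**Working it through.** The plan gives no response rate, power or precision figure to reproduce. The only sample size it derives is the Part 1 maximum in Section 8.1 (4 dose groups × 6 subjects = 24), which is correct but has no bearing here.

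**1. Can the sequence occur?** Count days back from the first dose.

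| Event | Day | Rule | Met? |
|---|---|---|---|
| Standard-of-care scan | -28 | Section 5.12: at most 28 days before treatment | Yes |
| Last chemotherapy | -15 | Criterion 17: none within 14 days | Yes |
| Consent and Screening | -14 | Section 6.7.2: ban starts here | Yes |
| First AGI-134 dose | 0 | Appendix B, Section 2: scan within 4 weeks | Yes |

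**2. How long is the interval?** Let *s* be the scan day and *t* the day of last therapy, both in days before dosing. The scan precedes therapy when *s* > *t*.

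- Chemotherapy, targeted small molecules, radiotherapy: *s* ≤ 28 and *t* ≥ 15. The longest gap is 28 − 15 = 13 days. Scan days 16 to 28 are affected (13 of them), giving 1 + 2 + … + 13 = 91 day combinations.
- If therapy exactly on Day -14 is allowed, the longest gap is 28 − 14 = 14 days.
- Antibodies and experimental agents: *t* ≥ 28 at the least, so *s* > *t* is impossible and the gap is 0 days.

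**3. How much does it lower the bar for partial response?** Let *c* be the fractional shrinkage from the earlier treatment after the scan. The further shrinkage needed from the first dose is 1 − 0.70/(1 − *c*).

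| *c* (assumed) | Further shrinkage needed |
|---|---|
| 0% | 30% |
| 10% | 22.2% |
| 15% | 17.6% |
| 20% | 12.5% |
| 30% | 0% |

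**4. Examples (assumed sizes).**

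- False response: 100 mm at the scan, 80 mm at first dose, 68 mm at Week 9. From the scan, (68 − 100)/100 = −32%, partial response. From the first dose, (68 − 80)/80 = −15%, stable disease.
- Masked progression: 100 mm, 80 mm, then 96 mm. From the scan, −4%, stable disease. From the first dose, +20% and +16 mm, progression.

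**5. Effect on a reported rate.** One false responder among the approximately 35 Part 2 subjects adds 1/35 = 2.9 points. The documents give no frequency, so take an assumed range: 5% to 30% of subjects have such a baseline, and 5% to 30% of those reach partial response through carry-over.

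- Expected false responses: 35 × 0.05 × 0.05 = 0.09, up to 35 × 0.30 × 0.30 = 3.15.
- Chance of at least one: 1 − (1 − 0.0025)^35 = 8%, up to 1 − (1 − 0.09)^35 = 96%.

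This range is wide enough to show only that the effect could be negligible or material.

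**The case against.** Several points on the other side are sound and limit the concern.

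- **Radiotherapy is largely guarded.** A reader might infer that irradiating the un-injected lesion would pass as an abscopal effect. The documents do not support that as a general statement. Appendix B, Section 1.3.3, usually treats irradiated lesions as not measurable without shown progression, and the footnote to inclusion criterion 3 takes the same line for eligibility. If the lesion is irradiated after the only scan, no later image can show progression. Some discretion remains, because the appendix rule is not absolute and neither text says that progression must follow the latest course. Chemotherapy and targeted therapy have no such guard.
- **Section 6.7.2 and criterion 17 do not conflict.** A reader might see two different cut-off dates as a contradiction. One is a prohibition on study and the other an eligibility washout. Both apply, and an exclusion window does not permit what another section prohibits. The effect of Section 6.7.2 is to confine the gap essentially to scans taken before consent.
- **The melanoma sub-population of about 10 is less exposed.** One false responder there would add 1/10 = 10 points. However, Section 8.2 defines the group by prior checkpoint inhibitors, and the 28-day antibody window leaves no gap for those. Only additional chemotherapy or targeted therapy could create one.
- **There are other checks.** Superficial lesions are photographed before the first dose (Section 5.3.1), and the sponsor approves eligibility (Section 5.1). Neither replaces the RECIST baseline sum, and no written rule tells the sponsor to reject such a scan. Appendix B also wants the baseline near treatment start. A Day -28 scan fits that poorly when a later one is feasible, but the stated limit of 4 weeks is met.
- **The Imaging Manual may contain the missing rule.** Sections 5.1 and 5.12 both refer to it, and it is not among the documents. This cannot be settled here.

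**Conclusion.** The gap stands. For a subject scanned before consent and then given chemotherapy or targeted therapy, shrinkage from that treatment could be counted towards response to AGI-134, or could mask progression. The interval is at most 13 whole days, or 14 on the looser reading of the washout. It does not arise for antibodies or experimental agents, and it is mostly closed for radiotherapy.

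The consequence is confined to efficacy, which Section 8.2.1.3 makes exploratory. The primary objective of safety, MTD and RP2D is unaffected. The list of exploratory endpoints is not legible, so it is assumed that RECIST response is among them. The carry-over sizes and frequencies above are assumptions. The documents support saying that this could happen under the stated time limits, not that it will happen or how often. Within those limits it is worth correcting, because the bias in response runs towards benefit and the correction is cheap.

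**What to change.** In Sections 5.1 and 5.12, accept a pre-consent scan as the RECIST baseline only if it was taken after the last dose or fraction of any prior anti-cancer therapy. Otherwise, perform the scheduled Screening scan and use it. This removes all 91 day combinations counted above and leaves the washout windows as they are. With last therapy on Day -15, 15 days remain in which to obtain a valid scan.

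For subjects already enrolled whose baseline scan preceded their last prior therapy, report response with and without them. Treatment history is collected at Screening, so they can be identified if the scan date and last treatment date are both held in the eCRF.

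The cost is one sentence in each of two sections, and a few subjects who cannot reuse an older scan. If the Imaging Manual already has this rule, it is enough to state it in the protocol.
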